In the current study, we will examine how the *Surviving and Thriving in the Real World (STRW)* intervention improves the DLS of 72 adolescents with ASD in their last 2 years of high school. Our previous work has found that STRW can increase the DLS of adolescents with ASD by 2-2.5 years over the course of the intervention, which has significant and practical implications for both current functioning (e.g., maintaining a part-time job while in high school, managing a checking and savings account, cooking meals for oneself) and future adult outcomes (e.g., budgeting for monthly expenses, keeping one's apartment clean, making routine medical appointments, planning for meals for an entire week and then going grocery shopping). The current study will examine these outcomes and also explore how factors such as social-communication skills (e.g., understanding expectations, taking others' perspectives), executive functioning abilities (e.g., getting started on tasks, organizing, managing time), and parenting and family factors (e.g., parental stress, over-involvement in daily routines) may affect one's ability to acquire DLS.

PURPOSE OF STUDY:

The main objective of the current proposal is to conduct a pilot RCT (i.e., treatment group and social skills control group) to examine how participation in STRW affects proximal outcomes with a larger sample size (n = 70). As social skills, executive functioning, and parenting factors have been linked to the acquisition of DLS, the current study will also explore how these are linked to participation in STRW. Lastly, goal attainment scaling (GAS) will be utilized, along with gold standard parent report and adolescent self-report measures, to assess DLS.

Aim 1: Examine the effectiveness of Surviving and Thriving in the Real World (STRW) in a pilot RCT. Participants will be randomized to STRW or a social skills control group (Program for the Evaluation and Enrichment of Relational Skills-PEERS). The STRW group will show significant improvement on the Vineland Adaptive Behavior Scales, 3rd Edition (Vineland-3) and progress on targeted DLS using goal attainment scaling (GAS), baseline to post-treatment, as compared to the control group.

Aim 2: Assess the maintenance of treatment gains 6-months after completion of STRW. Participants in the STRW group will continue to show significant improvement on the Vineland-3 and progress on targeted DLS using GAS, baseline to 6-month follow-up, as compared to the control group.

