
STUDY DESIGN:

Pilot RCT of Surviving and Thriving in the Real World (STRW): The pilot RCT will consist of running 5 cohorts of 16-20 high functioning adolescents with ASD (IQ≥70) and their parents in a

STRW treatment group or social skills control group. Once an eligible cohort of 16-20 adolescents with ASD has been recruited, adolescents will be randomly assigned to either the STRW group or control group using a stratified randomized block design with IQ as a strata variable (IQ<85 and IQ≥85) to ensure balanced group assignment for each cohort. Approximately 8-10 adolescents with ASD and their parents will participate in each STRW group. Thus, across 5 cohorts, the goal will be to enroll at least a total of 70 adolescents in the study, 35 in the STRW group and 35 in the control group across Years 1-3.

SELECTION AND RECRUITMENT OF PARTICIPANTS:

Inclusion Criteria

The inclusion criteria for the 70 adolescent participants include the following: between the ages of 15-22, in the last 2 years of high school (i.e., in the 11th or 12th grade or has deferred their high school graduation); a diagnosis of ASD (based on clinical judgement and/or meeting the cut-off score on the Autism Diagnostic Observation Schedule, 2nd Edition; ADOS-2)(Lord et al., 2012); a full scale IQ of 70 or above as measured by the Stanford Binet Intelligence Scales, 5th Edition (SB-5)(Roid, 2003); and deficient DLS as assessed by the Vineland Adaptive Behavior Scales, 3rd Edition(S. Sparrow, Cicchetti, & Saulnier, 2016) (Vineland-3; i.e., at least 1 of the 3 Daily Living Skills subdomains is at least 15 points below their full scale IQ).

Exclusion Criteria

Exclusion criteria include significant aggressive behaviors or mental health issues that require treatment out of the scope of the current intervention. Information about medication usage and services/therapies received at home, school, or community will be collected at each assessment. Also, if the adolescent has already completed the social skills group (PEERS), either at Cincinnati Children's or in another setting, they will not be eligible for the study unless it has been a significant amount of time since they did the PEERS group (2-3 years, or up to the discretion of the PI). In these cases, the parent must give verbal understanding that their child may be randomized to the social skills group.

Recruitment

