or the ADOS-2, either clinically or for a previous study, record of this exam including scoring may be utilized in this project if the results are considered acceptable for use by the Principal Investigator (i.e., completed within the last 2 years, completed by a psychologist who is research reliable on the ADOS-2). The parent participants will complete the Vineland-3 to confirm that their adolescent has deficient daily living skills (i.e., 15 points below their full scale IQ in 1 of the 3 Daily Living Skills subdomains) and a clinical interview that assesses specific daily living skills that will be targeted in the STRW intervention. The baseline assessment will include parent questionnaires, a parent interview, and an adolescent assessment (in which they will also complete questionnaires) and will take approximately 2-3 hours for both parent and adolescent participants to complete. All procedures for the baseline visit except for the ADOS and the IQ test may be conducted via telehealth. Information about medication usage and services/therapies received at home, school, or community will be collected at each assessment. The parent interview will be audio or video taped to assist in the development of goals using the method of goal attainment scaling (GAS). If inclusion criteria is met, participants will then be randomized to either the STRW group or the social skills group.

Post-Treatment and 6-Month Follow-up.

The post-treatment and 6-month follow-up assessments will include parent questionnaires, a parent interview, and adolescent questionnaires and will take approximately 60-90 minutes for both parent and adolescent participants to complete. All procedures for the post-treatment and 6 month follow up visits may be conducted via telehealth. Information about medication usage and services/therapies received at home, school, or community will be collected at each assessment. The parent interview will be audio or video taped to assist in the development of goals using the method of goal attainment scaling (GAS).

The STRW treatment group and the PEERS control group will complete 3 research assessments (baseline, post treatment, and 6 month follow up).

12-Month, 18-Month, and 24-Month Parent Follow-Up

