The entire study will last from October 2018 through December 2022. Participant recruitment and randomization will begin in October 2018. The duration of the study per participant randomized to either STRW or the control group is approximately 12 months. Data collection will be completed by [name] and approved research personnel. Data analysis and reporting of results pertaining to the primary aims of the current study are expected to continue through December 2022.

DATA ANALYSIS/METHODS:

Data Entry Procedures

Physical data, including test protocols that are collected at CCHMC will be housed in locked file cabinets in the PI's lab space. This space will be locked at all times. Only the principal investigator or other IRB approved members of the CCHMC research team will have access to the physical data.

All data for each participant will be labeled with a unique ID number. Source documents and protocols may be scanned to a PDF and stored as an electronic file in the secured CCHMC server. Data will be entered into REDCap, a secure, web-based application designed to support data capture for research studies, providing: 1) an intuitive interface for validated data entry; 2) audit trails for tracking data manipulation and export procedures; 3) automated export procedures for seamless data downloads to common statistical packages; and 4) procedures for importing data from external sources.

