A secure REDCap⁸⁰ database has been built and will be maintained for all measures administered in the current study. The primary analysis will be conducted with an intent-to-treat approach. The primary outcome measures for Objectives 1 and 2 at post-treatment and 6-month follow-up are (1) change in Vineland-3 DLS domain raw score and age equivalent score and (2) change in score on the goals targeted on the DLS-GAS. We will also evaluate the Vineland-3 subdomain raw scores and age equivalent scores. The expectation is that the STRW group will have an increased change in score on both the Vineland-3 and DLS-GAS as compared to the control group. All analyses will be done using SPSS Version 20.0. Univariate statistics such as means, medians, and standard deviations will be computed for each variable to allow for examination of any outliers, variables that are not normally distributed, and heterogeneous variance between groups. The comparability of the two groups in some measured baseline covariates prior to treatment will be assessed using chi-square tests for categorical variables and t-tests for continuous variables. Variables found to be non-normal will be transformed using appropriate functions to confirm with the normality assumptions.

To test Aim 1: Initially a two-sample t-test will be used to test the difference on the change scores in the Vineland-3 DLS domain and GAS (post-treatment and baseline) between the STRW and control groups. Although this is a randomized study it is possible that some of the demographic variables might be differentially distributed between the groups. In this case, the initial analysis will be followed by a general linear regression analysis where cohort will be treated as the main effect and other differentially distributed variables will be added to the model as possible confounders in order to investigate the independent effect of the intervention group on outcome.

To test Aim 2: The within-subject change between post-treatment and 6-month follow-up for each individual receiving the intervention will be calculated and a paired t-test will be conducted to evaluate this change (post-treatment and 6-month follow-up).

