Aim 1: For each DLS subdomain, we anticipate that adolescents in the STRW group will have a mean improvement of 9 months (a mean gain in age equivalence of 9 months) at post-treatment compared to a mean improvement of 4 months in the control group. Assuming a conservative pooled standard deviation of 8.4, we will have 80% power to detect the above effect size (of 0.71) with 32 participants per group. We will have 90% power to detect an effect size of 0.82 (a 9.9-month difference in the change of age equivalents between groups).

Aim 2: For each DLS subdomain, we anticipate that all participants, after receiving the STRW treatment, will maintain treatment gains from post-treatment to 6-month follow-up.

FACILITIES and PERFORMANCE SITES:

The Division of Behavioral Medicine and Clinical Psychology (BMCP) at Cincinnati Children's Hospital Medical Center (CCHMC) will serve as the project site for the recruitment and assessment of participants for the study. Assessment rooms (approximately 225 sq. ft.) within DDBP will be used for the assessments. The video and audio recording equipment needed for the project will be housed in this space for the duration of the project.

The in-person STRW and control group sessions will be held in the Schubert Research Clinic through the Clinical Translational Research Center (CTRC) in the T building on CCHMC's campus. We will use 2 conference rooms for the parent and adolescent weekly meetings. We will be using the Metabolic kitchen for the cooking portion of the STRW group.

POTENTIAL BENEFITS:

We hope that all participants in the intervention group will benefit greatly from the individualized intervention in daily living skills provided in this study. We also hope it may increase skills in other areas and by incorporating parental involvement, potentially directly affect current functioning and future adult outcomes by increasing capabilities for skills that are needed to succeed in college, employment, and independent living. Further potential benefits for those enrolled in the PEERS intervention include hopefully improving the participant's social skills. However, it is important to

emphasize that this study is being conducted for research purposes and does not ensure better or safer treatment nor guarantee individual benefits to the participant. Participants will receive monetary compensation for their time spent completing the study protocol.

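### Aim 2 claims an STRW-versus-control effect at 6 months, but the only test planned for it is a paired t-test within STRW, with no criterion for maintenance

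*Combined protocol and SAP*

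**What the plan says.** Under Purpose of Study, Aim 2 is comparative: the STRW group should show improvement on the Vineland-3 and on goal attainment scaling, "baseline to 6-month follow-up, as compared to the control group". The Analyses section gives this time point primary status: "The primary outcome measures for Objectives 1 and 2 at post-treatment and 6-month follow-up are" change in the Vineland-3 DLS domain and change on the DLS-GAS. It adds that STRW is expected to change more than control.

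The same section then sets out the tests. For Aim 1: "Initially a two-sample t-test will be used to test the difference on the change scores", limited to post-treatment minus baseline, with a follow-on regression if demographic variables are unbalanced. For Aim 2, the change from post-treatment to 6 months is calculated in those who received the intervention, and "a paired t-test will be conducted to evaluate this change (post-treatment and 6-month follow-up".

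Under Sample Size and Power Calculations, the Aim 2 entry says only that participants, once treated with STRW, "will maintain treatment gains from post-treatment to 6-month follow-up". No margin, decision rule or power figure is attached. The control arm is followed to the same point: "The STRW treatment group and the PEERS control group will complete 3 research assessments", the third being the 6-month visit (Post-Treatment and 6-Month Follow-up).

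**The concern.** The Aim 2 test differs from the Aim 2 hypothesis in two ways. It has no control comparator, and it measures from post-treatment rather than from baseline. An analyst who followed the plan would report no between-arm test or effect estimate at a time point the plan calls primary.

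The two questions can have different answers. The power section expects gains of 9 months in STRW and 4 in control by post-treatment, an advantage of 9 − 4 = 5 months. Suppose, as an assumption, that STRW then stays at 9 while controls gain another 4. The advantage falls to 9 − 8 = 1 month. The paired test would correctly find no loss in STRW, and no planned test would show that most of the advantage had gone.

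The paired test does suit the narrower durability question in the power section. Without a criterion, however, a reader cannot tell which result counts as maintained, and a non-significant result is not evidence of no loss.

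**Working it through.** **1. Hypothesis and tests side by side.**

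| | Aim 2 as stated | Test given for Aim 2 | Test given for Aim 1 |
|---|---|---|---|
| Comparator | Control arm | None | Control arm |
| Window | Baseline to 6 months | Post-treatment to 6 months | Baseline to post-treatment |
| Who | STRW and control | Recipients of the intervention | STRW and control |

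Nothing else fills the gap. The Aim 1 follow-on regression extends the same post-treatment analysis. The Aim 3 regression also models post-treatment minus baseline. The sentence on the expected direction names no method. Restricting the paired test to recipients also sits poorly with the intent-to-treat statement in the Analyses section. This step needs no numerical assumption.

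**2. The plan's own power figure.** It concerns Aim 1 only: 80% power, effect size 0.71, 32 per group. Alpha is not stated; two-sided 0.05 is assumed throughout. With noncentrality d × √(n/2) = 0.71 × √16 = 2.84 on 62 df, power is 0.798, so the figure reproduces. The raw inputs do not give that effect size: (9 − 4)/8.4 = 0.595, whereas 0.71 × 8.4 = 5.96 months. That is a separate inconsistency, so both values are carried forward.

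**3. What a non-significant paired test would mean (illustration).** Inputs: n = 35, from Study Design ("35 in the STRW group and 35 in the control group"), with no dropout. The documents give no SD for post-treatment-to-6-month change, so 8.4 is borrowed from Aim 1 and varied from 4.2 to 12. The losses examined are 5 months (the expected advantage) and half of that, 2.5.

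SE = SD/√n = 8.4/√35 = 1.42. Noncentrality = 2.5/1.42 = 1.76 on 34 df. The 95% CI half-width is 2.03 × 1.42 = 2.89 months.

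| SD (months) | Power, 2.5-month loss | Non-significant | 95% CI half-width (months) |
|---|---|---|---|
| 4.2 | 0.928 | 7% | 1.44 |
| 8.4 | 0.402 | 60% | 2.89 |
| 12 | 0.224 | 78% | 4.12 |

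A 5-month loss would usually be detected: power 0.928 at SD 8.4 and 0.668 at SD 12.

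**4. Power of the missing between-arm test.** Assume the Aim 1 effect and SD carry over to 6 months. For a 5-month difference at 35 per arm, SE = 8.4 × √(2/35) = 2.01 and noncentrality = 5/2.01 = 2.49 on 68 df.

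| Assumed effect | 32 per arm | 35 per arm |
|---|---|---|
| 5 months, SD 8.4 (d = 0.595) | 0.650 | 0.690 |
| Stated d = 0.71 | 0.798 | 0.833 |
| 2.5 months, SD 8.4 | 0.216 | 0.233 |

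For 5 months at 35 per arm, power is 0.930 at SD 6 and 0.405 at SD 12. If only 25 per arm were analysed (SD 8.4), it would be 0.541 for d = 0.595 and 0.691 for d = 0.71.

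**The case against.** The strongest reply is that this is a pilot, run to learn what differences in DLS to expect. Power was planned for Aim 1 alone, the Aim 1 comparison is intact, and the power section treats Aim 2 as a question of durability, which a paired test fits. That reading is fair for the power section. It does not remove the comparative wording of Aim 2 or the primary status of 6-month change, and pilot status does not explain following controls to 6 months without a planned comparison.

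A second reply is that group summaries would still show the 6-month picture. The Analyses section does plan means and SDs for each variable, but to check outliers, normality and variances. That supplies no specified effect estimate or test.

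The third reply has more force: a formal loss margin is more than a pilot needs, and the illustration rests on a borrowed SD for subdomain age equivalents, giving a range of 7% to 78%. The margin is indeed secondary. An interval reported without a claim of maintenance would be enough. The figures show only that non-significance alone cannot establish maintenance; the main finding does not depend on them.

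**Conclusion.** The point holds and should be fixed. As written, the plan states a between-arm hypothesis for baseline to 6 months, calls the 6-month change primary, and specifies no test of it. This follows from the text alone.

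The absence of a maintenance criterion is a lesser, linked defect. Its size depends on an SD the documents do not give: a true 2.5-month loss would pass as non-significant about 60% of the time at SD 8.4, and between 7% and 78% over SDs of 4.2 to 12, with 35 analysed and two-sided 0.05.

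**What to change.** Rewrite the Aim 2 paragraph so that its test compares baseline-to-6-month change between arms, in the Vineland-3 DLS domain and the DLS-GAS, in all randomised participants. Missing 6-month values would be handled by the multiple imputation already planned. The simplest version applies the Aim 1 two-sample comparison. Adding the baseline score as a covariate is preferable, and one repeated-measures model with arm contrasts at both visits would also serve. Name one of these as the analysis, and say whether the domain result is judged on raw or age-equivalent scores, since the plan lists both.

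Keep the within-STRW change from post-treatment to 6 months as an estimate with a 95% CI. Claim maintenance only if that interval excludes a loss margin, set by the sponsor for each scale before the 6-month data are analysed. Without such a margin, report the interval and make no claim.

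The cost is a short SAP change and no new visits. The limits should be stated:

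- Between-arm power at 35 per arm is about 69% for 5 months at SD 8.4, 83% at d = 0.71, and 23% if only 2.5 months of advantage remain.
- A tight margin is out of reach. With SD 8.4, no true change and 80% power, the normal approximation n = (8.4 × (1.96 + 0.84)/margin)² gives 35 for a 4-month margin but 89 for 2.5 months.
- The document is dated November 2022, and the Duration section says analysis and reporting for the "primary aims of the current study are expected to continue through December 2022". If the 6-month data have been seen, label the comparison a late amendment and do not apply a margin chosen afterwards.
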